Our main hypothesis is that we can reduce all-cause mortality to 11.2% by measuring suPAR on admitted patients. Using a 5 % level of significance and a power of 80 %, we will need a sample of 7340 patients in each randomization group to detect this difference an absolute risk reduction in mortality at least 10 months after admission of 1.5 %.

Based upon numbers from the two emergency departments, approximately 170 patients are admitted on a daily basis. During the inclusion period it will be possible to collect data on 10,700 patients in both active- and control periods. This will be sufficient to assess the primary hypothesis.

Ethics and approvals

The study was approved by the board of directors at each participating hospital and department heads of the emergency departments gave consent. The study was presented to the Regional Ethics Committee, who decided that no formal approval was needed in accordance with Danish law (Jr. Nr.: FSP-15003590). All processing of personal data followed national guidelines in accordance with Danish law and the study was approved by the Danish Data Protection Agency (HGH-2015-042, I-Suite nr.04087) and will be registered at the Danish Patient Safety Authority. The study is registered at clinicaltrials.org (NCT02643459).

Economy

Expenses related to the study are financed by ViroGates A / S. Together with ViroGates external funding will be sought for parts of or the entire project.

References

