Kaplan-Meier plots will be used to illustrate survival. Unpaired T-test will be used to compare length of stay. $P < 0.05$ will be considered significant.

Subgroup analysis of the following groups will be performed: patients aged 65 year and above, and patients discharged with diagnoses of surgical conditions, cancer, infections, and cardiovascular disease.

Final Statistical analysis plan

April 5 2017

This document contains the statistical analysis plan for the TRIAGE III trial. The statistical analysis plan has been completed prior to the availability of the outcome data. The plan was made available on April 5 2017 on a public website:

<https://www.hvidovrehospital.dk/afdelinger-og-klinikker/Klinisk-Forskningscenter/om-centret/Til-forskere-paa-hospitalet/Documents/TRIAGE%20III%20Analysis%20plan.pdf>
and at clinicaltrials.gov.

Time-line:

Study start: January 11 2016. Study completion: June 6 2016. **The primary analysis will be conducted 10 months after inclusion of the last patient**, which is expected to be April 6 2017.

Background:

The primary research question is: **Can the introduction of a prognostic biomarker strengthen risk stratification of acutely admitted patients leading to fewer deaths.** The study is a cluster randomized controlled interventional trial conducted at two major emergency departments of unselected patients acutely admitted.

Design:

Cluster-randomized, cross-over, parallel interventional two center trial, conducted around six cycles of three weeks in a 1:1 allocation ratio of intervention versus control at each cluster.

Inclusion:

1. ≥ 16 years at admittance.
2. Acute arrival at the emergency department within the inclusion period.
3. Have routine blood tests analyzed, including hemoglobin, C-reactive protein, and creatinine, within 6 hours of admission to the emergency department.

4. As the results of the blood tests can take up to two hours to provide, the doctors cannot change outcome based on biomarker levels until those data are provided. Hence, inclusion time will be calculated as time for blood sampling + 2 hours.

Exclusion:

1. Arrival at the gynecological-, obstetric-, and pediatric department.

Ethics:

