The study was presented to the Regional Ethics Committee, who decided that no formal approval was needed in accordance with Danish law. The study has been approved by the Danish Patient Safety Authority (3-3013-1744/1) and data management has been approved by the Danish Data Protection Agency (ID: HGH-2015-042, I-suite: 04087).

Study variables and endpoints:

The following data are collected for the included patients:

- Age
- Results of the routine blood tests at the index admission including suPAR where available. Routine biomarkers: Hemoglobin, Leukocytes, thrombocytes, sodium, potassium, C-reactive protein, Creatinine, ALAT, Albumin, Calcium, lactate. suPAR in intervention periods
- Gender
- Personal Identification number (Danish Civil Registration number (CPR))
- At follow-up (10 months after inclusion of last patient) the following data is collected from the National Patient Registry (NPR)
- Contacts with the hospital system (including all historical contacts)
- Information regarding admissions (date, time and place of admission and discharge)

- Diagnoses (follow-up during study period, historical and in relation to index admission)
- Date of death or immigration (only very few immigrations are expected)
- Charlson score will be calculated using registered diagnoses in NPR dating two years back from index admission

Sample size calculation

In a previous unpublished study of patients acutely admitted to an Emergency Department in Denmark 12-month mortality was 12.7% and readmission rate was 16% within 5 months. Using a 5% level of significance and a power of 80%, the study will need to include 7,340 patients in each group to detect an absolute risk reduction in mortality of 1.5% at 10 months after admission. The two participating hospitals approximately admit 170 patients on a daily basis. During the study period approximately 10,700 patients will be included in every group.

Study end

The follow-up for all patients ends at April 6 2017 and this date will be used as the censoring time for the main analysis.

Statistical plan for main outcome paper

Statistical analyses will be performed using SAS and R.

Consort diagram:

A modified CONSORT trail profile will be used to describe patient flow and total number patients in each group. All patients not included in analysis will be explained.

Baseline description of groups:

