Table of summary statistics for each group (described separately for each hospital in appendices) will be presented with a number of baseline variables (age, sex, results of routine blood tests, comorbidities).

Continuous variables will be summarized with: n (non-missing sample size), mean, standard deviation, median, interquartile range, number of missing values. Categorical variables will be reported as frequency and percentages (based on non-missing sample size) and number of missing values.

Continuous and ordinal variables will be tested by Wilcoxon analysis for differences between groups. Categorical variables will be tested with chi-square.

Primary outcome analysis:

The primary outcome will be an **analysis of all-cause mortality between the intervention and control groups**. Patients will be followed as one cohort and data will be analyzed as randomized. Patients will be included at their first contact with the emergency department (index admission) and are followed until the April 6 2017. Any patient lost to follow-up will be censored at the last time known to be alive.

Patients admitted in the intervention period without a suPAR measurement will remain in the intervention group for analyses corresponding to the intention-to-treat principle.

The main analysis of the primary outcome will use a weighted Cox model to compare the primary outcome of all-cause mortality. Patients are artificially censored if they are readmitted at one of the study emergency departments in the opposite group of their index admission. As this censoring is likely to be dependent censoring (a readmission is rarely a positive prognostic signal), we will employ Inverse Probability of Censoring Weighting (IPCW) where patients readmitted to their own treatment group will be up-weighted to compensate. We will employ stabilized weights such that the reweighted sample has the same implied sample size throughout follow-up. Due to the design, time since index admission is the only covariate that needs to be included in the weights. Reweighting will be done for every two weeks of follow-up. We will not censor nor reweight for 2nd or later readmissions, since the weights would become highly unstable and it is not likely that the presence or absence of an initial suPAR measurement will be important for clinical decisions at this stage.

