A secondary analysis will be performed where the observational period ends if a patient is readmitted within the inclusion period. We anticipate, that the patients in the secondary analysis will seem healthier and the possible effect of the intervention weaker, although showing the same trend as the main analysis. Notable difference between the results of the main and the secondary analysis strategies will be considered critically.

Finally a per protocol weighted analysis is planned. In this analysis, only patients with a suPAR measurement are included in the intervention group. In order to investigate the difference between these results and the main analysis, we will analyze the mortality differences between patients with and without a suPAR measurement in the intervention periods.

Kaplan-Meier plots will be used to illustrate survival. Robust standard errors will be employed to account for the clustering. $P < 0.05$ will be considered statistically significant

Adjusted analyses of primary endpoint:

Three additional models will also be examined to further examine any role of differences in baseline values of the two groups. The first will include age, sex, CRP and center. The second will further include Charlson score. The third will include all variables used in the descriptive statistics. Results will be presented as hazard ratios with 95% confidence intervals. A forest plot will illustrate the results.

Sensitivity analyses of the primary endpoint:

Sensitivity analyses will be performed: One analysis where all readmissions are censored and a second analysis with only 10 months follow-up for all patients.

Secondary endpoints:

The predefined secondary endpoints of the study are: all-cause mortality at one month of admission; short admission (<24 h) to the emergency department; admission to the medical wards; admission to the intensive care unit; new (not previously registered) cancer diagnosis at the end of the study; length of stay during admission; readmission at one and three months; and economical expenses.

All-cause mortality at one month will be analyzed similar to the primary outcome. The discriminative ability of suPAR with regard to mortality at one and ten months will be assessed by using area under the curve for receiver operating characteristics curves as well as sensitivity, specificity, negative- and positive predictive value. To compare

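### The deciding mortality model names no baseline covariate, although age, sex, CRP and center are available and already listed for an additional model; on the age split alone this gives up about 7-10% of individual-level information

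*Combined protocol and SAP*

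**What the plan says.** Final SAP, Primary outcome analysis: "The main analysis of the primary outcome will use a weighted Cox model to compare the primary outcome of all-cause mortality". The section describes artificial censoring at a crossover readmission and the inverse-probability weights that compensate for it. Time since index admission enters those weights only. No baseline covariate and no stratification by hospital is named, so the deciding comparison is by clear implication arm-only, although the SAP never says so in those words.

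Final SAP, Adjusted analyses of primary endpoint, introduces its models this way: "Three additional models will also be examined to further examine any role of differences in baseline values of the two groups". On their content it says: "The first will include age, sex, CRP and center". The second model adds the Charlson score, and the third adds every variable in the baseline table. All are to be reported as hazard ratios with 95% confidence intervals in a forest plot.

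Final SAP, Inclusion, requires patients to "Have routine blood tests analyzed, including hemoglobin, C-reactive protein, and creatinine, within 6 hours of admission to the emergency department", so CRP is present by definition. Age is needed for the 16-year criterion, sex is a collected variable, and the hospital is known by design. None of the four depends on the suPAR result.

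Final SAP, Sample size calculation: "Using a 5% level of significance and a power of 80%, the study will need to include 7,340 patients in each group". It expects about 10,700 per group.

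**The concern.** Age is a very strong predictor of death in the documents' own cohort. Leaving a strong predictor out of a Cox model pulls the estimated hazard ratio toward 1 and lowers the power of the test, even when the arms are perfectly balanced. The trial also compares only 12 hospital-periods (2 hospitals x 6 periods), so case mix can differ between arms by chance and pass directly into an unadjusted hazard ratio.

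The sponsor has already chosen suitable covariates and written the model down. What is at stake is which model settles the trial. If the arm-only and adjusted results fall on opposite sides of P = 0.05, the SAP as written gives the decision to the less precise one.

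**Working it through.** **1. The plan's own figure.** Inputs: final SAP, Sample size calculation ("12-month mortality was 12.7% and readmission rate was 16% within 5 months" and an "absolute risk reduction in mortality of 1.5% at 10 months after admission"), and final protocol, Power calculation ("reduce all-cause mortality to 11.2% by measuring suPAR on admitted patients"). Two-sided 5%, 80% power, pooled variance, no continuity correction:

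n = [1.960 x sqrt(2 x 0.1195 x 0.8805) + 0.842 x sqrt(0.127 x 0.873 + 0.112 x 0.888)]² / 0.015² = 7,340 per group.

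This matches exactly. The same formula gives 92.3% power at 10,700 per group. It has no term for clustering. Under proportional hazards the target hazard ratio is ln(0.888)/ln(0.873) = 0.875.

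**2. Strength of age.** Original protocol, Figure 1 (the suPAR risk table), 90-day deaths summed over the suPAR rows:

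- below 70 years: 14 + 27 + 15 + 21 = 77 of 2,652 = 2.9%
- above 70 years: 12 + 125 + 96 + 76 = 309 of 1,691 = 18.3%

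Hazard ratio = ln(1 - 0.183)/ln(1 - 0.029) = 6.9. Share above 70 = 1,691/4,343 = 38.9%.

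**3. Information lost by omitting age.** Take the covariate as independent of arm and the treatment effect as small. At a given baseline cumulative hazard, let m and v be the mean and variance of the relative hazard among survivors. The unadjusted log hazard ratio is then shrunk by the factor 1 - (cumulative hazard x v/m). Averaged over events this is A, and the loss is 1 - A².

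| Overall mortality | A | Loss |
|---|---|---|
| 8.9% (Figure 1, 90 days) | 0.964 | 7.1% |
| 12.0% (same hazard ratio carried forward) | 0.950 | 9.8% |
| 12.7% (same hazard ratio carried forward) | 0.946 | 10.4% |

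Simulation check on the two-group age case at 7,340 per arm: mean z was -2.79 unadjusted and -2.95 adjusted, so the efficiency ratio is (2.95/2.79)² = 1.12. The loss is 1 - 1/1.12 = about 11%, which agrees.

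**4. All four covariates.** The documents give no joint prognostic strength, so this step is an assumption. With a normally distributed log-hazard score at 11.95% mortality, the formula gives:

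| Assumed AUC | Loss |
|---|---|
| 0.70 | 7% |
| 0.72 | 9% |
| 0.75 | 12% |
| 0.77 | 15% |
| 0.80 | 22% |

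For comparison, the age split alone, carried to 12.0% mortality, has an AUC of 0.73.

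**5. Effect on power, age alone.** A loss L makes the adjusted test act like n/(1 - L) patients.

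| Per group | No adjustment | L = 7% | L = 10% |
|---|---|---|---|
| 7,340 | 80.0% | 82.8% (acts like 7,892) | 84.0% (acts like 8,156) |
| 10,700 | 92.3% | 93.9% (acts like 11,505) | 94.6% (acts like 11,889) |

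**6. Chance imbalance.** Carrying the age hazard ratio to 12.7% overall mortality gives 4.3% below 70 and 25.9% above, a gap of 21.6 points. A 1-point difference between arms in the share over 70 then moves mortality by 0.01 x 21.6 = 0.22 points, and 0.22/1.5 = 14% of the target. With independent patients, the standard error of that difference in shares is sqrt(2 x 0.389 x 0.611/10,700) = 0.67 points. A 1-point gap is therefore 1.5 standard errors, which is unremarkable even before extra variation between periods.

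**The case against.** **The adjusted models are pre-specified.** They will be shown beside the main result, and baseline tables are planned by group and by hospital. A reader might infer that adjustment was overlooked. It was not, and an imbalance would be visible. What remains is that these models do not decide the result.

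**The loss is not a documented figure.** Only the age split comes from the documents. It describes 90-day deaths among medical patients at one hospital, whereas this trial also admits surgical patients and follows them for about 10 to 15 months. This stands. A larger single figure for all four covariates would be assumption presented as fact, so a range is given.

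**The trial is not short of power.** A reader might infer that the arm-only model puts the trial at risk of missing its effect. At 10,700 per group the plan's formula already gives 92.3%, and age adds only about 2 points. This stands, with one qualification: that formula ignores clustering, so the real margin is unknown.

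**This is not bias.** The schedule in the final protocol's Figure 1 gives each hospital three periods in each arm, and each calendar period has one hospital in each arm. Stable hospital differences and shared calendar effects are largely balanced. Only chance hospital-by-period case mix is left. A one-year gap in mean age would move the hazard ratio much further, but the documents give no reason to expect it. With an assumed age SD of 20 years, the standard error of the difference is 20 x sqrt(2/10,700) = 0.27 years without clustering.

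**Clustering and weighting were not modelled.** The calculations use independent patients without censoring weights. This stands: the gain is in individual-level information, and it need not carry over in full where variation between periods drives the variance.

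**The marginal hazard ratio is a legitimate target.** It is, and adjustment changes the target to a conditional one. That calls for a statement in the SAP. It is not a reason to give up precision.

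**Conclusion.** The point holds as a moderate, nearly free improvement, not as a flaw that invalidates the analysis. The deciding model leaves out four prognostic variables that are in hand and already chosen.

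The size supported by the documents' own data is about 7% of individual-level information at 90 days. It is about 10% if the age hazard ratio of 6.9 persists to about 12 months and applies to this trial's wider population. The 7-22% for all four covariates depends wholly on the assumed AUC of 0.70-0.80. The gain in power is modest at the planned enrolment. The protection against ordinary case-mix differences between 12 hospital-periods is a second, separate reason to adjust. The documents do not support a claim of systematic bias or of inadequate power from this cause.

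**What to change.** Before outcome data are available, reword the Primary outcome analysis section so that the already planned model with age, sex, CRP and center decides the mortality comparison. Center may enter as a covariate or as a stratum. Keep the same censoring weights and robust standard errors. Fix in advance how age and CRP enter, since the SAP does not say. Retain the arm-only weighted model as a supportive analysis in the same forest plot. One-month mortality, which the SAP analyzes like the primary outcome, would follow.

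The cost is SAP wording only: no new data and essentially no patients lost. The one downside is that the hazard ratio becomes conditional on the covariates and is expected to lie slightly further from 1 than the marginal one. The SAP and the report should describe it that way.

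### The supportive per-protocol analysis compares only measured intervention patients with all controls, so it is biased if having a suPAR result is related to prognosis

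*Combined protocol and SAP*

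**What the plan says.** The final SAP, under Primary outcome analysis, describes the main analysis as a weighted Cox comparison in which "Patients admitted in the intervention period without a suPAR measurement will remain in the intervention group for analyses corresponding to the intention-to-treat principle". The same section then adds a weighted per-protocol analysis as the last of the planned analyses: "In this analysis, only patients with a suPAR measurement are included in the intervention group". It states no corresponding rule for the control group.

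To help explain any divergence from the main result, it also plans that "we will analyze the mortality differences between patients with and without a suPAR measurement in the intervention periods".

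The only weights described are inverse-probability-of-censoring weights for a readmission in the opposite group. Of these the SAP says: "Due to the design, time since index admission is the only covariate that needs to be included in the weights".

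Under Study variables and endpoints, the listed biomarkers include "suPAR in intervention periods", so control patients have no suPAR result at their index admission.

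Under Inclusion, both groups must "Have routine blood tests analyzed, including hemoglobin, C-reactive protein, and creatinine, within 6 hours of admission to the emergency department", and "inclusion time will be calculated as time for blood sampling + 2 hours".

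**The concern.** The randomised comparison is between periods. The per-protocol rule removes part of one side, chosen by something that happens after arrival, and leaves the other side whole. The control patients who would have gone unmeasured had they come in an intervention period cannot be identified, so they stay in. If unmeasured patients are sicker than average, the remaining intervention patients look better than controls with no effect of suPAR. If they are healthier, the bias runs the other way.

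Nothing specified elsewhere corrects this. The censoring weights depend on time since index admission and carry no information on who was measured. The covariate-adjusted models are not tied to the per-protocol analysis. The comparison of measured with unmeasured patients can show that the groups differ, but it cannot separate selection from an effect of measuring. The SAP also leaves open what weighted means for this analysis, and whether unmeasured patients are dropped (the natural reading) or moved to the control group.

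At stake is how a supportive result is read. The SAP's only stated significance threshold is 0.05 and the contrast has no descriptive label, so it could be taken to confirm or contradict the main result.

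**Working it through.** **Inputs from the documents** (final SAP, Sample size calculation, and final protocol, Power calculation): control mortality 12.7%, target 11.2%, hence a 1.5-point difference; 5% significance; 80% power; 7,340 needed and about 10,700 expected per group. The 12.7% is a 12-month figure that the plan itself uses for planning.

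**Inputs assumed:** the unmeasured share *u* (2%, 5%, 10%) and mortality among the unmeasured *m* (20% or 5%). The documents give neither. The test is taken as two-sided.

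**Step 1: reproduce the plan's figure.** With pooled variance, no continuity correction and mean proportion 0.1195:

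n = [1.960·√(2·0.1195·0.8805) + 0.8416·√(0.127·0.873 + 0.112·0.888)]² / 0.015² = 7,340 per group.

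This matches exactly, and the present point does not change it.

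**Step 2: spurious difference with no true effect.** Both arms have 12.7% mortality overall. Mortality in the measured patients is (0.127 − *u·m*)/(1 − *u*). For *u* = 0.10 and *m* = 0.20 this is (0.127 − 0.020)/0.90 = 0.1189, against 0.127 in controls: −0.81 points, or 54% of the 1.5-point target.

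**Step 3: rejection rate.** The measured group has 10,700·(1 − *u*) patients and the control group 10,700. For the case above, SE = √(0.1189·0.8811/9,630 + 0.127·0.873/10,700) = 0.0046. The shift is 0.0081/0.0046 ≈ 1.76 standard errors, so P(|Z| > 1.96) ≈ 0.42.

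| Unmeasured | Their mortality | Measured mortality | Spurious difference | Rejection |
|---|---|---|---|---|
| 2% | 20% | 12.55% | −0.15 points | about 6% |
| 5% | 20% | 12.32% | −0.38 points | about 13% |
| 10% | 20% | 11.89% | −0.81 points | about 42% |
| 2% | 5% | 12.86% | +0.16 points | about 6% |
| 5% | 5% | 13.11% | +0.41 points | about 14% |
| 10% | 5% | 13.56% | +0.86 points | about 44% |

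**Step 4: cross-checks.** A null simulation (20,000 replicates, patients independent) with 10% unmeasured and twice the mortality of the measured rejected in 71% of per-protocol contrasts. Keeping everyone in the allocated group rejected in about 5%. When unmeasured and measured patients had equal mortality, the per-protocol contrast also stayed at about 5%. For selection alone to produce the full 1.5 points at 10% unmeasured, their mortality would have to be (0.127 − 0.90·0.112)/0.10 = 26.2%.

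**Step 5: the alternative under the same null.** The as-randomised difference divided by the measured fraction is 0/0.90 = 0, so the selection drops out. Ignoring clustering and weights, its standard error at 10% unmeasured is √(2·0.127·0.873/10,700)/0.90 = 0.0046/0.90 = 0.0051, about 10% wider than the naive contrast.

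**The case against.** The strongest reply is that little depends on this analysis. It is supportive, no decision rule uses it, the main analysis keeps every unmeasured patient, and the SAP already plans a diagnostic comparison. All of that stands. It limits the weight of the point but does not make the contrast valid.

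The second reply is that the documents weaken the likely routes to selection.

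- Both groups need routine bloods within six hours, and suPAR uses 10 µl of excess plasma from routine bloods. Death or discharge after sampling does not by itself prevent a measurement.
- Time zero at sampling plus two hours, in both groups, limits bias from very early death.
- The final protocol gives a capacity of at least nine tests an hour with staff present around the clock. Figure 1 shows one active hospital per period. With 170 daily admissions split evenly (an assumption), load averages 170/2/24 ≈ 3.5 an hour, so routine overload is not shown.

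These safeguards reduce selection but do not remove it, because eligible patients can still lack a result and the SAP provides for them.

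Third, the rejection rates treat patients as independent and use a two-proportion test. The plan specifies a weighted Cox model with robust standard errors, so these are not the planned test's error rates. That is correct. The spurious differences do not depend on clustering.

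A reader might also infer that the SAP presents this analysis as the effect among patients who received the test. It does not; it states no estimand for it.

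**Conclusion.** The point holds as a conditional one about a supportive analysis. Followed as written, the per-protocol contrast is biased whenever having a suPAR result is related to prognosis, and neither the defined weights nor the planned diagnostic corrects it. The direction is unknown. The size runs from negligible (about 0.15 points at 2% unmeasured) to more than half the target effect (about 0.8 points at 10%), under assumed shares and mortality, 12.7% overall mortality, 10,700 per arm and independent patients.

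A reader might go further and infer that the trial's primary conclusion is compromised, or that its false-positive rate is above 40%. The documents support neither. The main analysis does not restrict on measurement, and the 42% to 44% figures belong only to the per-protocol contrast in assumed scenarios. Nor do the documents show that early death, rapid discharge or workload actually decides who is measured. A change is worth making, but it leaves the primary analysis and sample size as they are.

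**What to change.** In the final SAP, under Primary outcome analysis:

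1. Report the fraction of intervention-period patients with a suPAR measurement at index admission, overall and by hospital.
2. Label the per-protocol contrast and the measured-versus-unmeasured comparison as descriptive. Say what weighted means for the former, and that unmeasured patients are left out of it, not moved to control.
3. Base any statement about the effect in measured patients on a complier-average estimate. This is the 10-month risk difference between allocated periods, from the same crossover-censored, IPCW-weighted data as the main analysis, divided by the fraction measured at index admission in intervention periods. Derive its interval from that as-randomised difference.
4. State two conditions. Compliance is defined at index admission, because control patients can be readmitted during an intervention period and non-compliance is one-sided only at the index visit. An intervention period is assumed to affect mortality only through a reported result.

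The cost is some SAP wording and one risk-difference analysis beyond the planned hazard ratio, using data already collected. The interval is wider than that of the naive contrast and one assumption is added. The estimate rescales the as-randomised result, so it gives no independent test. Weighting measured patients by their probability of measurement, from the baseline variables collected, is an alternative, but it assumes those variables capture the selection.

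### With two hospitals, one unqualified sentence on robust standard errors does not secure the 5% level of the primary test, and the stated power makes no allowance for clustering

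*Combined protocol and SAP*

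**What the plan says.** Under Primary outcome analysis, the final SAP states: "The main analysis of the primary outcome will use a weighted Cox model to compare the primary outcome of all-cause mortality". The model uses inverse probability of censoring weights (IPCW). No hospital or period term, and no stratification, is stated for it. Clustering is covered by one sentence, "Robust standard errors will be employed to account for the clustering", and significance is judged at 5%.

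Hospital enters only the additional models under Adjusted analyses: "The first will include age, sex, CRP and center". The original SAP does not mention clustered standard errors.

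The Design section describes a two-centre crossover "conducted around six cycles of three weeks in a 1:1 allocation ratio of intervention versus control at each cluster", so its word for the hospital is cluster. The Time-line section gives "Study start: January 11 2016. Study completion: June 6 2016". The Sample size section says "the study will need to include 7,340 patients in each group" for 80% power at the 5% level, and then "During the study period approximately 10,700 patients will be included in every group".

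**The concern.** A sandwich (robust) variance is justified when there are many clusters. Here there are two hospitals or, if the hospital-period is the unit, 12 cells. At these numbers the uncorrected variance is unstable, and a normal critical value is not calibrated to it. The choice of unit therefore changes the answer materially, and the SAP does not make that choice.

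The primary P value and confidence interval rest on it. The same data could give quite different P values under choices that would all comply with the text. The sample size has a related problem: it treats patients as individually randomised and tests against a normal reference, so the stated 80% does not describe a test whose degrees of freedom come from a few hospital-periods.

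**Working it through.** **Inputs from the documents.** Two hospitals; six periods in strict alternation (Figure 1 of the final protocol); 10,700 per group, so 21,400/12 = 1,783 patients per hospital-period; mortality 12.7% against 11.2% (mean 11.95%); 5% level; 80% power.

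**Assumed.** Between-hospital, shared-period and hospital-period SDs on the log-risk scale, because the documents give none. The calculations use binary risk differences, without the Cox model or the IPCW weights. Simulations used 40,000 null trials per scenario.

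**1. The plan's own figure.** Two-sided two-proportion formula with pooled null variance:

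n = [1.960·√(2·0.1195·0.8805) + 0.842·√(0.127·0.873 + 0.112·0.888)]² / 0.015² = 7,340 per group.

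This matches the SAP exactly and contains no clustering term.

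**2. Number of periods.** Six cycles × 21 days = 126 days. January 11 to June 6 2016 is 147 days = 7 × 21. Enrolment: 170 × 126/2 = 10,710 per group, which fits the stated 10,700; 170 × 147/2 = 12,495 does not. The figures below use six periods.

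**3. True level at nominal 5%, critical value 1.96.**

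(a) *Clustered on hospital.* Let d₁ and d₂ be the active-minus-control differences in the two hospitals. The estimate is (d₁+d₂)/2 and the sandwich SE is |d₁−d₂|/(2√2). Their ratio is √2 times a Cauchy variable, so P = 1 − (2/π)·arctan(1.96/√2) = 0.398. Shared calendar variation enters d₁ and d₂ with opposite signs, which inflates the SE. The level falls to about 29% and 18% at shared-period SD 0.05 and 0.10.

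(b) *Clustered on the 12 hospital-periods, treatment-only model (simulated).*
- No hospital or period differences: about 10%.
- Hospital SD 0.05: about 7%; with hospital-period SD 0.05 added, about 8%.
- Hospital SD 0.10: 4.6%.
- Shared-period SD 0.10 alone: 1.2%.

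With hospital and categorical period terms added but no correction, 12 − 8 = 4 residual df remain and the variance is too small by a factor of 3. Then P(|t₄| > 1.96/√3) = 0.32.

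(c) *Patient-level.* The true variance exceeds the assumed one by r = 1 + 1,783·(SD·0.1195)²/(0.1195·0.8805), and the level is P(|Z| > 1.96/√r).
- SD 0: r = 1, level 5%.
- SD 0.05: r = 1.60, level about 12%.
- SD 0.10: r = 3.42, level about 29%.

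**4. Power with matching degrees of freedom, no extra between-period variation.** SE = √[(0.127·0.873 + 0.112·0.888)/n]. At n = 10,700 this is 0.00443, noncentrality 0.015/0.00443 = 3.38. At n = 7,340 it is 0.00535, noncentrality 2.80. With hospital and categorical periods the df are 4. With a linear time trend they are 12 − 4 = 8.

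| n per group | normal | t(8) | t(4) |
|---|---|---|---|
| 10,700 | 92% | 84% | 72% |
| 7,340 | 80% | 69% | 56% |

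Hospital-period variation lowers these further. At 10,700 and assumed SD 0.03 and 0.05, power is about 64% and 53% with t(4), and 77% and 65% with t(8). The t(8) advantage needs calendar change to be close to linear: at irregular shared-period SD 0.10, its power is 34%, against 71% with t(4).

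**The case against.** The strongest reply is that the SAP is under-specified, not wrong: it does not say that the sandwich is uncorrected or that the hospital is the unit. That stands. A reader might infer that this trial has a 40% false-positive rate, and the documents do not support that. The figure needs hospital clustering, no correction, a normal reference and no shared calendar variation all at once.

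A reader might also infer the opposite, that hospital-period clustering is simply conservative and the main harm is lost power. That is not supported either. At hospital SD 0.05 the level is still about 7%. It reaches or falls below 5% only with hospital SD near 0.10 or shared period variation. Without variance components, the direction of the error is unknown.

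The t(4) analysis is not assumption-free. It holds about 5% only if hospital-period errors are independent. At hospital-period SD 0.10 it gives about 3% with lag-1 correlation 0.5 and about 9% with −0.3. Figure 1 alternates strictly, so the documents do not show hospital-periods being randomised independently. Taking them as the unit is a modelling choice that has to be stated.

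Planned enrolment is 10,700/7,340 = 1.46 times the stated requirement, so the power figures at 7,340 test the SAP's 80% statement and do not describe the planned trial.

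None of this supplies the missing unit, correction or reference distribution.

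**Conclusion.** The concern holds, and it should be resolved before the primary analysis. The single sentence on robust standard errors leaves the level of the primary test open. Clustering on hospital, the most literal unit given the Design section's wording, fails from having two clusters alone. The other two readings reach 5% only under particular values of unknown variation. Over the assumed range, the uncorrected versions run from about 1% to about 40%.

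The 80% power at 7,340 per group is valid only for individually randomised patients and a normal test. At the planned 10,700, power is about 72% with t(4), or about 84% with t(8) if calendar change is close to linear, before any hospital-period variation.

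The two-cluster and 32% levels are closed-form results for balanced cells. The other levels depend on assumed SDs, and none of the figures includes the Cox model or its weights. They should be read as orders of magnitude. No seven-period power is given, because the layout is unsettled and unequal groups would change it.

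**What to change.** Amend the SAP before outcome data are seen:

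1. Reconcile the number and layout of periods: six cycles, 126 days and 10,700 per group against dates that span seven 21-day periods. The degrees of freedom depend on this.
2. State the unit used for inference, for example the hospital-period, and the hospital and calendar-time terms in the primary model, including whether time is categorical or linear.
3. Prespecify a small-sample method with matching df. One example is a weighted analysis of hospital-period estimates with hospital and period effects and a t reference (4 df with six categorical periods), with its assumption of independent hospital-period errors stated. A small-sample-corrected sandwich or another valid method would also serve if fixed in advance.
4. Do not base the primary P value on an uncorrected sandwich.
5. Restate power under the chosen method, and give seven-period power only once the layout is settled.

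The cost is SAP wording and some analysis code. No new patients are needed. The stated power will be less favourable, and because inclusion has closed, sample size cannot make up the difference.
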